Hypothesis	The primary hypothesis of this study is that using HeartFlow's FFR _{CT} analysis as part of the treatment pathway for clinically stable, symptomatic patients with suspected CAD in the ED/observation unit can result in a more streamlined diagnostic pathway and therefore provide cost-effective clinical care for patients.
Population	The population for this study will be clinically stable, symptomatic patients who present to the ED or observation unit with suspected CAD and no history of coronary artery disease, and who while in the ED or observation unit have a CCTA performed which shows at least one $\geq 40\%$ lesion and no lesions $> 90\%$ in a major epicardial vessel, and a successfully processed FFR _{CT} (if applicable).

Study Design and Methods	
This is a prospective multi-center study. All clinically stable, symptomatic patients who present to the ED or observation unit with suspected CAD and who have at least one $\geq 40\%$ lesion and no lesions $< 90\%$ lesion in a major vessel, confirmed by CCTA, are eligible for enrollment once their CCTA has been completed and FFR_{CT} (if applicable) has been ordered. All enrolling sites will have CCTA incorporated into their standard evaluation of chest pain in the ED/observation unit. Non-control sites will have CCTA and FFR_{CT} analysis incorporated into their standard evaluation of chest pain in the ED/observation unit.
 
All sites will provide demographics, medical history, CCTA images, FFR_{CT} (for non-control sites), the decision plan post CCTA and pre FFR_{CT} (for non-control sites), length of stay for patients in the ED/observation unit/hospital, billing reports (UB-04 preferred), 30-day clinical outcomes, and any other hospital or office visits, imaging, and/or procedural data completed prior to the follow-up 30-day visit.
 
Sites which do not have FFR_{CT} incorporated into the ED/observation unit will be control sites. If FFR_{CT} is implemented at a control site during the enrollment period, the site can request to switch over to the non-control arm once FFR_{CT} has been successfully implemented in the ED/observation unit at that site. This switch must be reviewed and approved by the HeartFlow Clinical Research team.

Primary Endpoint	The primary endpoint of ADVANCE-ED is the reclassification rate between the coronary management plan based on the review of the CCTA compared to the actual management.

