Acute chest-pain syndromes are the second most common reason for emergency department (ED) visits with more than 6.5 million such visits occurring annually in the United States.

Although acute coronary syndrome (ACS) is ultimately diagnosed in only 5.1% of patients who present with chest pain, many of these patients are admitted to hospitals, at an estimated cost of over \$3 billion annually (1,2). In addition, patients with chest pain return for additional care within one week at a rate of up to 10% (3). This places additional strain on EDs and hospitals.

Recent updates to the guidelines for acute chest pain management in the emergency department setting place CCTA as a 1A “for intermediate-risk patients with acute chest pain and no known CAD”. Further, FFR_{CT} was given 2aB-NR as an add-on diagnostic test “for intermediate-risk patients with acute chest pain and no known CAD, with a coronary artery stenosis of 40% to 90% in a proximal or middle coronary artery on CCTA. FFR_{CT} can be useful for the diagnosis of vessel-specific ischemia and to guide decision-making regarding the use of coronary revascularization” (1).

In the ED, coronary computed tomography angiography (CCTA) is a beneficial noninvasive technique for use in patients with acute chest pain, due to its high accuracy for detection of coronary artery disease (CAD); however, an increase in CCTA can often be followed by an increase in invasive coronary angiography (ICA) (4). With increasing health care expenditures, there is ever-expanding focus on appropriate resource utilization. To that end, the historically high rates of nonobstructive disease at the time of ICA are being increasingly scrutinized.

HeartFlow, Inc. (‘HeartFlow’) provides a non-invasive method to determine the hemodynamic significance of CAD (FFR_{CT}) from subject-specific CCTA data using computational fluid dynamics under simulated maximal coronary hyperemic conditions (5). Results from two prospective trials suggest that FFR_{CT} accurately predicts the hemodynamic significance of coronary lesions when compared to invasively measured FFR (6,7). FFR_{CT} is available in Japan, in many European countries (CE mark 2011), in Canada, and in the U.S. (De Novo 510K clearance 2014).

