- Cost utility analysis to include length of stay, secondary coronary testing, and invasive coronary procedures
- Major Adverse Coronary Event (MACE) rates at day 30
- Rate of invasive catheterization without obstructive disease at day 30
- Time to diagnosis
- Time to discharge

IV. STUDY DESIGN

All non-invasive and invasive data collected will be obtained from clinical practices that are standard clinical care. All details about cardiovascular testing and treatment (planned and actual) will be recorded at baseline.

IV. A. Location and Number of Subjects

Approximately 500 subjects will be enrolled from approximately 20 experienced clinical research sites across the US.

All enrolling sites will have CCTA incorporated into their standard evaluation of chest pain in the ED/observation unit. Approximately half of the sites will be FFR_{CT} sites who will have CCTA and FFR_{CT} analysis incorporated into their standard evaluation of chest pain in the ER/observation unit. Sites who have CCTA but not FFR_{CT} incorporated into the ED/observation unit will be control sites.

If FFR_{CT} is implemented at a control site during the enrollment period, site can request to switch over to the non-control arm once FFR_{CT} has been successfully implemented. This switch must be reviewed and approved by the HeartFlow Clinical Research team.

No site may enroll more than 75 (15%) subjects in the trial.

IV. B. Patient Population

The population for this study will be clinically stable, symptomatic patients who present to the ED or observation unit with suspected CAD and while in the ED or observation unit, have a CCTA performed which shows at least one >40% lesion and no lesions >90% in a major epicardial vessel, a successfully processed FFR_{CT} (if applicable), and no history of coronary artery disease.

IV. C. General Inclusion and Exclusion Criteria

Inclusion Criteria (all must be present):

1. Age ≥18 years
2. Clinically stable, symptomatic patients who present to ED/observation unit with suspected CAD
3. CCTA shows at least one >40% lesion and no lesions >90% in at least one major epicardial vessel
4. FFR_{CT} processed successfully (if applicable)
5. EKG with no acute ischemic changes
6. Willing to comply with all aspects of the protocol, including adherence to follow up visit
7. Agrees to be included in the study
8. Able to provide written informed consent

Exclusion criteria (all must be absent):

1. CCTA showing no >40% lesion in a major epicardial vessel

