2. CCTA showing a lesion >90% in a major epicardial vessel
3. CCTA showing other incidental, non-cardiac findings requiring admission, i.e., pneumonia or pulmonary embolism
4. Uninterpretable CCTA which is not of diagnostic quality
5. CABG or PCI prior to CCTA acquisition
6. Left main lesion >50%
7. Confirmed of acute coronary syndrome (acute myocardial infarction or unstable angina)
8. Known complex congenital heart disease or any history of coronary artery disease
9. Patients with tachycardia or significant arrhythmia which cannot be adequately controlled with medications to allow CTA
10. Any active, serious, life-threatening disease with a life expectancy of less than 2 months
11. Inability to comply with follow-up requirements
12. Currently enrolled in another study utilizing FFR_{CT} or in an investigational trial that involves a non-approved cardiac drug or device
13. Persons under the protection of justice, guardianship, or curatorship

V. STUDY WORKFLOW

The workflow for ADVANCE-ED is described in the following sections.

V. A. Study/Site Selection

HeartFlow will identify and qualify the clinical research sites for ADVANCE-ED. Participating sites will be screened for:

- CCTA acquisition practices conforming to SCCT guidelines
- Adequate resources and past clinical research experience
- HeartFlow's ED Connect in active use and an ED/observation unit pathway including CCTA and FFR_{CT} in place for non-control sites
- An ED/observation unit pathway including CCTA for control sites

V. B. Subject Selection

Institutional review board approval will be obtained at all participating sites prior to screening patients. All patients who meet all inclusion criteria and do not meet any exclusion criteria, and are able and willing to participate, are candidates for ADVANCE-ED. All patients providing written informed consent and meeting all selection criteria will be enrolled into the study.

V. C. Screening Period

1. All subjects must fulfill all study inclusion criteria and no study exclusion criteria.
2. Each subject will undergo the following assessments to be documented in the appropriate electronic case report form (eCRF) upon enrollment:
 - a. Collection of demographic information
 - b. A summary of the subject's relevant medical history and cardiovascular risk factors
 - c. Information about the subject's CCTA results
 - d. Information about the subject's FFR_{CT} results (non-control sites)

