 - e. Decision plan prior to FFR_{CT} results (non-control sites)

V. D. Enrollment

All subjects must provide written informed consent prior to enrollment. A notation will be made in the subject's medical chart, if required by the institution, and in the study records that he/she is participating in the study, has had his/her questions answered, has read, signed, and dated the Informed Consent Form (ICF), and been given a copy of the ICF.

All subjects who meet eligibility requirements will be asked to participate. Subjects will be considered enrolled in the study after the following criteria have been met:

1. Informed consent form has been signed and subject has been provided a copy.
2. All inclusion criteria and no exclusion criteria have been met.

V. E. Follow up

A 30 day (± 7 days) follow up phone call with the subject following baseline visit will be done as a part of this study. Data collected will include:

- Current cardiac health status
- Any additional hospital admissions

- Any additional ED/observation unit visits
- Any cardiac procedures/tests
- MACE

Sites will also be asked to provide billing information (UB-04 preferred) from baseline to day 30. Reports and images for CCTA, FFR_{CT} (if applicable), ICA, and other cardiac tests will be uploaded to the eCRF.

VI. STUDY DURATION

The anticipated enrollment duration of ADVANCE-ED will be approximately 18 months. A 30 day follow up phone call is planned for this study.

VI.A. Rules for Subject Withdrawal

Each subject is free to withdraw from the study at any time. No additional data will be collected after a subject informs the Investigator that they want to withdraw.

VI. B. Rules for Terminating the Study

There are no formal termination criteria for this study. The sponsor reserves the right to terminate ADVANCE-ED at any time. Investigators have the responsibility to comply with all applicable regulatory guidelines and regulations. Specific reasons which may cause the sponsor, the Institutional Review Board, or local regulatory authorities to terminate a center include, but are not limited to:

- 1) Failure of the investigator to comply with investigator agreement, protocol, guidelines, and/or regulations.
- 2) Serious protocol violations.
- 3) Submission of knowingly false information from the research facility to the sponsor, clinical monitor, or other party involved in the study.

VI. C. Rules for switching from Control arm

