Sites who do not have FFR_{CT} incorporated into the ED/observation unit will be control sites. If FFR_{CT} is implemented at a control site during the enrollment period, site can request to switch over to the non-control arm once FFR_{CT} has been successfully implemented. This switch must be reviewed and approved by the HeartFlow Clinical Research team.

VI.D. SAFETY ASSESSMENT

Patients will undergo a clinically indicated CCTA and any other invasive physiological measurements, which do not require additional radiation, extra contrast, or additional procedure time for this study/protocol. All procedures performed will be per standard clinical care, and data obtained will be documented as per standard of clinical care. Therefore, there will be no additional clinical risks for subjects who participate. MACE will be collected at day 30. MACE is defined as the composite rate of all cause death, non-fatal myocardial infarction (MI) and unplanned hospitalization for acute coronary syndrome (ACS) leading to urgent revascularization.

VI.E. RATIONALE AND ETHICAL CONSIDERATIONS

This prospective, multi-center study is being conducted to provide real world evidence potentially in support of including FFR_{CT} in an ED pathway.

The potential risks to subjects participating in this study include potential breach of confidentiality. Data transmitted to HeartFlow will not contain any PHI identifiers and will be coded with a unique identifier for each subject. All applicable study data will be transferred to HeartFlow and core laboratories in a secure manner and in accordance with all applicable regulations.

Anticipated benefits

There are no specific benefits to subjects participating in the study. There may be some benefit to other patients who undergo FFR_{CT}-guided management in the future.

Anticipated risks

ADVANCE-ED is a prospective study which collects data from clinically-indicated CCTA imaging and other procedures. These procedures will have been planned as part of routine clinical practice; therefore, no additional clinical risks are related to participating in the study.

IX. STATISTICAL CONSIDERATIONS

IX. A. General Considerations

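### A control site that starts FFRCT in its ED stays control until a requested switch is approved, and FFRCT use in control subjects has no assured record

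*Combined protocol and SAP*

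**What the plan says.** **Who is a control.** Status is set at site level. Section IV.A states: "Sites who have CCTA but not FFR_{CT} incorporated into the ED/observation unit will be control sites". Section VI.C and the synopsis also tie control status to the ED/observation unit. Section V.A screens control sites only for "An ED/observation unit pathway including CCTA for control sites" and asks nothing about FFRCT elsewhere in the hospital. The one exclusion criterion that names FFRCT (number 12) concerns enrollment in another FFRCT study, so FFRCT ordered in routine care is not excluded.

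**What happens when a control site adopts FFRCT.** Sections IV.A and VI.C say the "site can request to switch over to the non-control arm once FFR_{CT} has been successfully implemented", and the sponsor's clinical research group must approve. The synopsis adds that the implementation is in the ED/observation unit; IV.A and VI.C do not name the unit. No section says how subjects enrolled between go-live and approval are labelled.

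**What is recorded.** Section V.C item 2d collects "Information about the subject's FFR_{CT} results (non-control sites". The synopsis restricts the same data in the same way: "FFR_{CT} (for non-control sites), the decision plan post CCTA and pre FFR_{CT} (for non-control sites". Other sources are not restricted by site type. The synopsis asks all sites for "any other hospital or office visits, imaging, and/or procedural data completed prior to the follow-up 30-day visit". The opening of section IV has cardiovascular testing recorded at baseline. Section V.E collects "Any cardiac procedures/tests" at the day-30 call, asks for billing to day 30, and calls for upload of reports, including FFRCT where applicable and other cardiac tests.

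**What the control arm is for.** Section IX.D gives it about 250 subjects and a role in the secondary endpoints only.

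**The concern.** The switch rule and the control definition do not fit together. Once FFRCT is running in a control site's ED/observation unit, the site no longer meets the definition, yet the only stated consequence is an optional request that then waits on approval. Followed as written, the plan can place subjects who had FFRCT in the ED in the arm meant to represent an ED pathway without it.

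A second, softer point concerns the record. FFRCT is derived "from subject-specific CCTA data using computational fluid dynamics", so it can be run on the index scan without a new acquisition or visit. The item designed to capture it is switched off at control sites, and no section says how a control subject who receives FFRCT is classified or analysed.

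The between-arm results are at stake: cost utility, MACE, catheterization without obstructive disease, and times to diagnosis and discharge. A small or null difference could partly reflect FFRCT use under the control label, and readers would need to know how much of it there was.

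**Working it through.** **1. Definition against switch rule.**

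| Situation at the site | Meets the control definition? | Label under the switch rule |
|---|---|---|
| No FFRCT in ED/observation unit | Yes | Control |
| FFRCT live there, no request made | No | Control |
| FFRCT live there, request pending | No | Control |
| FFRCT live there, switch approved | No | Non-control |

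The second and third rows conflict. This needs no assumption about FFRCT use elsewhere in the hospital.

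**2. Would FFRCT in a control subject be recorded?**
- V.C item 2d and the matching synopsis item: no, by their own restriction.
- Synopsis imaging and procedure data, and baseline testing in section IV: possibly, since neither is limited by site type.
- V.E call: uncertain, because the subject may not know that a computation was run on an existing scan.
- V.E billing: possibly, but sites are only asked for it.
- V.E uploads: FFRCT is named where applicable. The same qualifier in inclusion criterion 4 evidently means non-control sites, so a control-site coordinator could skip it. The upload of other cardiac tests remains.

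Capture is therefore plausible but not assured.

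**3. The plan's own figure.** Section IX.D says 208 subjects give an exact 95% interval of width 0.14 at a proportion of 0.5. The Clopper-Pearson interval for 104 of 208 is 0.4301 to 0.5699, width 0.1399; 206 subjects give 0.1405. The figure reproduces. It concerns the FFRCT arm alone, so nothing here changes it.

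**4. Illustration of dilution.** The documents give no control-arm event rate, no power for the secondary endpoints and no rate of FFRCT use at control sites. All the rates below are assumptions. Let c be the fraction of controls who receive FFRCT, and suppose they then have the FFRCT-arm rate p2. The control rate becomes (1−c)p1 + c·p2, so the difference becomes (1−c)(p1−p2). With n = 250 per arm, two-sided 0.05, p1 now the diluted control rate and p̄ the mean of the two rates:

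power = Φ{[|p1−p2|√n − 1.96√(2p̄(1−p̄))] / √(p1(1−p1)+p2(1−p2))}

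| c | Difference, 20% vs 10% | Power | Difference, 15% vs 8% | Power |
|---|---|---|---|---|
| 0 | 10.0 points | 88.2% | 7.0 points | 69.0% |
| 5% | 9.5 | 85.2% | 6.65 | 65.1% |
| 10% | 9.0 | 81.7% | 6.3 | 61.0% |
| 20% | 8.0 | 73.3% | 5.6 | 52.3% |
| 30% | 7.0 | 63.0% | 4.9 | 43.3% |

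**5. How large c could be from one adopting site.** With about 250 controls at about 10 sites, an average site supplies 250/10 = 25 subjects, or 25/250 = 10% of the arm. A site at the cap of 75 supplies 75/250 = 30%. These are ceilings for a single site, not estimates: subjects enrolled before go-live are unexposed, and not everyone enrolled afterwards need have FFRCT.

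**The case against.** The strongest reply has three parts.

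**The data plan is wider than item 2d.** A reader might infer that FFRCT in control subjects would be invisible. The documents do not support that. Imaging and procedures to day 30, baseline cardiovascular testing, billing and uploaded reports are collected without restriction by site type, and billing and reports do not depend on what the subject knows. Item 2d is an enrollment item and does not define what is collected afterwards. This part stands; what remains is that none of these sources asks the question directly.

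**Later FFRCT may be usual care.** A reader might infer that any FFRCT in a control subject is contamination. But control status, the secondary objective in section II and the rationale in VI.E all concern FFRCT in the ED/observation pathway. In a comparison of pathways, FFRCT ordered on a ward or in a clinic can belong to the comparator. This also stands. It does not cover FFRCT given in the ED itself after go-live, and even usual-care FFRCT has to be counted, because the cost endpoint includes secondary testing.

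**The numbers are assumed.** The (1−c) formula supposes that later FFRCT acts as ED FFRCT does. FFRCT run after discharge cannot shorten a stay already recorded, so the formula does not carry over to every endpoint. That is correct, and the table only shows sensitivity.

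It can also be said that a site with FFRCT live in its ED is no longer a control by definition, and that continued control enrollment there is conjecture. But the switch rule is the operating instruction, and it sets no cutoff.

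**Conclusion.** The switch rule contradicts the control definition and should be corrected. The narrower recording item leaves FFRCT use in control subjects without an assured record, and no rule says how such subjects are handled. The effect is confined to the between-arm secondary endpoints; the primary endpoint is unaffected. The likely direction is toward no difference, provided FFRCT acts on exposed controls much as it does in the FFRCT arm. The size cannot be estimated from the documents, and it may be nil if no control site adopts FFRCT during enrollment. It would go too far to conclude that control-arm FFRCT is unmeasurable, or that the control arm is known to be contaminated.

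**What to change.** 1. In VI.C, IV.A and the synopsis, end control enrollment at a site on the date FFRCT goes live in its ED/observation unit, whether or not a switch is requested or approved. Name the ED/observation unit in all three places.
2. In V.C item 2d and V.E, record at every site, from the medical record, whether FFRCT was run on the index CCTA at any time to day 30, when, and in which setting.
3. In section IX, state that control subjects stay in their enrollment arm for the main comparison, and report the rate of FFRCT use among them.

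The cost is one eCRF item at control sites, a few sentences, and the few control enrollments that would have fallen between go-live and approval. An analysis that drops whole control sites because FFRCT exists elsewhere in the hospital is a matter of preference and is not needed to close this gap.

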The ROMICAT II trial showed that CCTA in the ED reduces cost and length of stay when compared to standard of care (8). Additional studies such as the PLATFORM (Prospective Longitudinal Trial of FFR_{CT}: Outcome and Resource Impacts Study) and CONSERVE (Coronary Computed Tomographic Angiography for Selective Cardiac Catheterization) trials have highlighted the potential for CCTA and FFR_{CT} to help inform ICA referral in an effective and safe fashion. Work by Chinnaiyan, et al done in the ED, went on to show that FFR_{CT} leads to cost savings with no increase in MACE, and a negative FFR_{CT} (suggestive of a non-hemodynamically significant lesion) is particularly useful in patients with >50% stenosis showing significantly lower revascularizations and costs (9).

The ADVANCE-ED study is a prospective multi-center study in which clinically stable, symptomatic patients who present to the ED or observation unit with suspected CAD will have at least one >40% lesion and no lesions >90% in a major vessel, confirmed by CCTA. All enrolling sites will have CCTA incorporated into their standard evaluation of chest pain in the ED. Non-control sites have CCTA and FFR_{CT} analysis incorporated into their standard evaluation of chest pain in the ED/observation unit. For non-control sites, the treating healthcare provider will be asked to provide a management plan prior to the results of the FFR_{CT} being available. Subjects will be followed up at 30 days, and data will be collected for

any additional testing, office visits, hospital admissions, procedures, and outcomes.

II. STUDY OBJECTIVE

Primary Objective

The primary objective of the ADVANCE-ED study is to compare decision plans prior to FFR_{CT} with the actual decision made after FFR_{CT}.

Secondary Objectives

The secondary objectives are to evaluate utility, clinical outcomes, and resource utilization when FFR_{CT} analysis is incorporated in the emergency department (ED) or observation unit for clinically stable, symptomatic patients with suspected CAD to further inform patients, health care providers, and other stakeholders about which technologies are most effective and efficient in the diagnosis and management of ACS and CAD.

III. STUDY ENDPOINTS

A. Primary Endpoint

The primary endpoint of ADVANCE-ED is the reclassification rate between the coronary management plan based on the review of the CCTA compared to the actual management.

B. Secondary Endpoints

The secondary endpoints include:

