Descriptive statistical methods will be used to summarize the data from this study, with confidence intervals and hypothesis testing performed for the primary and other selected efficacy endpoints. Unless stated otherwise, the term “descriptive statistics” refers to number of events (n), mean, median, standard deviation (SD), standard error, (SE) minimum, maximum, and coefficient of variation (CV) for continuous data and frequencies and percentages for categorical data.

All data collected during the study will be included in data listings.

Unless specified otherwise, all statistical testing will be two-sided and will be performed using an overall significance (alpha) level of 0.05.

All statistical analyses will be conducted with the SAS® System, version 9.4 or higher.

A statistical analysis plan (SAP) will describe the methods of data collection, validation, analysis, and reporting. The sections below provide a brief overview of statistical consideration for the study.

IX. B. Subject Characteristics

Subject accountability will be described, including number of subjects enrolled, number of subjects included in the analysis, and reasons for any subjects discontinued from the study or was not included in the analysis. Demographic information will be summarized using descriptive statistics. Sex and medical histories will be summarized by counts and percentages.

IX. C. Endpoint Analysis

The null hypothesis for the primary endpoint is that the reclassification rate between the coronary management plan based on the review of the CCTA compared to the actual

management after FFR_{CT} is obtained is zero. A one-sample exact binomial test will be used to analyze the primary endpoint. In addition, the proportion with reclassification along with the 95% exact confidence interval will be produced.

IX. D. Sample Size

FFR_{CT} arm: Approximately 250 subjects may be enrolled into this study. A sample size of 208 produces a two-sided 95% exact confidence interval with a width equal to 0.14 when the proportion with reclassification is 0.5.

Control arm: The control arm will contribute only to secondary endpoints and is therefore not included in the powering of the primary endpoint but will be the same size as the FFR_{CT} arm and will include approximately 250 subjects.

IX. E. Analysis Populations

All subjects who meet the study criteria, and who sign the written informed consent, are enrolled in the study.

X. DATA HANDLING AND QUALITY ASSURANCE

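### With no clear control-site post-CCTA plan and a single-arm primary endpoint tested against zero, the reclassification rate cannot separate changes due to FFRCT from changes made for other reasons

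*Combined protocol and SAP*

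**What the plan says.** **Objective and endpoint.** Section II sets out to "compare decision plans prior to FFR_{CT} with the actual decision made after FFR_{CT". Section III.A defines the primary endpoint as the "reclassification rate between the coronary management plan based on the review of the CCTA compared to the actual management". No rule ties a change to FFRCT, and III.A sets no time window for actual management.

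**Who records the plan.** Two places limit it to FFRCT sites: V.C, item 2e ("Decision plan prior to FFR_{CT} results (non-control sites"), and Section I ("For non-control sites, the treating healthcare provider will be asked to provide a management plan prior to the results of the FFR_{CT} being available"). Two others are less clear:
- The Synopsis (Study Design and Methods) lists "the decision plan post CCTA and pre FFR_{CT} (for non-control sites" among the data that all sites supply. The parenthesis may qualify the whole item or only its pre-FFRCT part.
- Section IV opens with "All details about cardiovascular testing and treatment (planned and actual) will be recorded at baseline", and names no arm.

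**Analysis.** IX.C sets the null reclassification rate at zero and uses a one-sample exact binomial test with an exact 95% interval. IX.D says "The control arm will contribute only to secondary endpoints and is therefore not included in the powering of the primary endpoint". None of the secondary endpoints in the Synopsis or III.B is a plan-versus-actual change rate.

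**The concern.** A plan made after CCTA can differ from what is finally done for reasons unrelated to FFRCT. The protocol itself expects further inputs after CCTA: secondary coronary testing is part of a secondary endpoint, and V.E collects later cardiac tests, visits and admissions to day 30. Changes prompted by any of these enter the numerator beside the changes that FFRCT prompted.

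The objective is framed as before versus after FFRCT, and VI.E says the study may support putting FFRCT into an ED pathway. Readers will therefore take the rate as a measure of what FFRCT changed. Without a background rate there is no reference point for that reading. About 250 control subjects are planned and their later care is already collected, so the plan is the only missing piece. It cannot be reliably reconstructed afterwards.

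**Working it through.** **1. Inputs from the documents.** FFRCT arm about 250, control arm about 250, precision n = 208 at a rate of 0.5, null rate 0, two-sided alpha 0.05 (IX.A, IX.C, IX.D); about 10 sites per arm (Synopsis).

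**Assumed, not in the documents.** Background change rate b of 10% to 30%; 25 subjects per site (250/10, equal sizes); ICC 0.05.

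**2. The plan's own figure.** The Clopper-Pearson interval for 104/208 is 0.4301 to 0.5699, width 0.1399. At n = 207 the width is 0.1402. So 208 is the smallest n with width at most 0.14, and the stated sample size reproduces. The sample size is not at fault.

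**3. What the test against zero detects.** Under a null of exactly zero, one changed plan rejects. If FFRCT has no effect and plans change for other reasons at rate b, then P(reject) = 1 − (1 − b)^n:

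| b | n = 208 | n = 250 |
|---|---|---|
| 1% | 87.6% | 91.9% |
| 2% | 98.5% | 99.4% |
| 5% | >99.9% | >99.9% |

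Rejection therefore says nothing about whether FFRCT caused the changes.

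**4. What the rate leaves open.** Take an observed rate of 50%, the value at which IX.D states its precision. If the arms are comparable, the part net of background is 50 − b:
- b = 10%: 40 points
- b = 20%: 30 points
- b = 30%: 20 points

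The planned analysis reports 50% in all three cases.

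**5. What the planned control arm could show.** With 250 per arm, the 95% half-width of the difference is 1.96 × √[(0.5 × 0.5 + b(1 − b))/250]:
- b = 10%: 1.96 × √(0.34/250) = 0.072
- b = 20%: 1.96 × √(0.41/250) = 0.079
- b = 30%: 1.96 × √(0.46/250) = 0.084

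**6. Site clustering.** Design effect = 1 + (25 − 1) × 0.05 = 2.2, so the effective n is 250/2.2 ≈ 114 per arm. Half-widths grow by √2.2 = 1.483, to about 0.107, 0.118 and 0.125. IV.A lets a site enroll up to 75, and unequal site sizes would widen these further.

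**7. Power for 50% v 30%** (two-sided 0.05, pooled variance under the null). Without clustering, the pooled rate is 0.4 and the null SE is √(2 × 0.4 × 0.6/250) = 0.0438. The SE under the alternative is √(0.46/250) = 0.0429, so z = (0.20 − 1.96 × 0.0438)/0.0429 = 2.66 and power is 99.6%. At an effective n of 114, power is 87%. With other assumed ICCs it is 98.6% (0.01), 96.6% (0.02) and 70.1% (0.10). If background were as high as 40%, beyond the range used here, power for 50% v 40% would be 61% without clustering and 33% at ICC 0.05.

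**The case against.** **Control plans may already be covered.** A reader might infer from item 2e that control sites record no plan at all. The documents do not settle that: the Section IV sentence, and one reading of the Synopsis parenthesis, could include them. This stands as a reason to reconcile the text. It does not remove the problem, because no control-site plan item or analysis follows from either sentence and IX.D keeps controls out of the primary endpoint.

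**The endpoint makes no causal claim.** The protocol never says that every change is due to FFRCT, and IX.C words the comparison as management after FFRCT is obtained. That brings the endpoint closer to the objective, but changes for other reasons are still counted. The rate and its exact interval remain valid as a description.

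**The direction of bias is not fixed.** It is tempting to say that the rate always overstates FFRCT's contribution. That is not shown. A later event can reverse an FFRCT-driven change, so that final management matches the plan and the case is missed. Overstatement is the likely direction only. How often plans change without FFRCT is not in the documents either, and confirmed ACS and acute ischemic EKG changes are excluded, so the background could be low.

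**Subtracting controls is imperfect.** Arms follow site practice, are not randomized, and sites may switch (VI.C). At FFRCT sites the test has already been ordered, so the plan there may be more provisional than a control plan. If FFRCT replaces tests that change plans at control sites, subtraction would understate its effect. These limits stand. They are why the difference belongs as a supporting estimate, and why the post-FFRCT decision should also be recorded.

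**Conclusion.** The concern holds as an attribution gap. The primary result is a single-arm change rate that pools FFRCT-driven changes with all others. Its test against zero would almost surely reject even if FFRCT changed nothing and only a few percent of plans changed for other reasons.

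On an assumed background of 10% to 30%, an observed 50% is consistent with a net 20 to 40 points, conditional on comparable arms. The size therefore rests on two things the documents do not supply: the background rate and the comparability of the sites.

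A reader might also infer that the planned control arm is simply large enough for the comparison. Without clustering the precision is good; with the assumed clustering it is moderate, and a background near 40% would leave the comparison underpowered. The gap should be closed before enrollment begins, or as early in it as possible.

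**What to change.** 1. In V.C, item 2e, and the Synopsis, have all sites record the same post-CCTA plan, in the same categories, before later test results are known. Bring the Synopsis parenthesis, the Section IV sentence and Section I into line.
2. In the FFRCT arm, also record the decision made after FFRCT. This gives the before/after comparison that Section II asks for without relying on comparable sites.
3. Keep the single-arm rate with its exact interval. Define discordance identically in both arms and add the FFRCT-minus-control difference, with its 95% interval, as a key supporting estimate. Adjust it for case mix and site clustering, analyze subjects at switching sites by the arm in force at their enrollment, and describe the comparison as non-randomized.

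**Cost.** A protocol amendment and a plan form at about 10 control sites. This is more than opening an eCRF page: V.C has these items documented at enrollment, so sites need a workflow that captures the plan before later results. Clinicians spend a little extra time per subject, and the headline figure may become less favourable. No additional subjects are required.
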